8.3.5.2. Exposure During Breastfeeding

An exposure during breastfeeding occurs if:

- A female participant is found to be breastfeeding while receiving or after discontinuing study intervention.
- A female is found to be breastfeeding while being exposed or having been exposed to study intervention (ie, environmental exposure). An example of environmental exposure during breastfeeding is a female family member or healthcare provider who reports that she is breastfeeding after having been exposed to the study intervention by inhalation or skin contact.

The investigator must report exposure during breastfeeding to Pfizer Safety within 24 hours of the investigator's awareness, irrespective of whether an SAE has occurred. The information must be reported using the CT SAE Report Form. When exposure during breastfeeding occurs in the setting of environmental exposure, the exposure information does not pertain to the participant enrolled in the study, so the information is not recorded on a

CRF. However, a copy of the completed CT SAE Report Form is maintained in the investigator site file.

An exposure during breastfeeding report is not created when a Pfizer drug specifically approved for use in breastfeeding women (eg, vitamins) is administered in accord with authorized use. However, if the infant experiences an SAE associated with such a drug administration, the SAE is reported together with the exposure during breastfeeding.

8.3.5.3. Occupational Exposure

An occupational exposure occurs when a person has unplanned direct contact with the study intervention, which may or may not lead to the occurrence of an AE. Such persons may include healthcare providers, family members, and other roles that are provided in the trial participant's care.

The investigator must report occupational exposure to Pfizer Safety within 24 hours of the investigator's awareness, regardless of whether there is an associated SAE. The information must be reported using the CT SAE Report Form. Since the information does not pertain to a participant enrolled in the study, the information is not recorded on a CRF; however, a copy of the completed CT SAE Report Form is maintained in the investigator site file.

8.3.6. Cardiovascular and Death Events (Not Applicable)

8.3.7. Disease-Related Events and/or Disease-Related Outcomes not Qualifying as AEs or SAEs (Not Applicable)

8.3.8. Adverse Events of Special Interest

Refer to Section 8.2.7 for definitions of adverse events of special interest (AESIs).

All AESIs must be reported as an AE or SAE following the procedures described in Section 8.3.1 through Section 8.3.4. An AESI is to be recorded as an AE or SAE on the CRF. In addition, an AESI that is also an SAE must be reported using the CT SAE Report Form.

8.3.8.1. Lack of Efficacy (Not Applicable)

This section is not applicable as the study intervention administered is not approved for use.

8.3.9. Medical Device Deficiencies (Not Applicable)

8.3.10. Medication Errors

Medication errors may result from the administration or consumption of the study intervention by the wrong participant, or at the wrong time, or at the wrong dosage strength.

Exposures to the study intervention under study may occur in clinical trial settings, such as medication errors.

Safety Event	Recorded on the CRF	Reported on the CT SAE Report Form to Pfizer Safety Within 24 Hours of Awareness
Medication errors	All (regardless of whether	Only if associated with an SAE
	associated with an AE)	

Medication errors include:

- Medication errors involving participant exposure to the study intervention;
- Potential medication errors or uses outside of what is foreseen in the protocol that do or do not involve the study participant.

For further clarification, a medication error is:

- Any preventable event causing or leading to inappropriate medication use or patient harm;
- When patient misunderstood, could not read, was not aware of, or not given dosing instructions.

Such medication errors occurring to a study participant are to be captured on the medication error page of the CRF, which is a specific version of the AE page.

In the event of a medication dosing error, the sponsor should be notified within 24 hours.

Whether or not the medication error is accompanied by an AE, as determined by the investigator, the medication error is recorded on the medication error page of the CRF and, if applicable, any associated AE(s), serious and non-serious, are recorded on an AE page of the CRF.

Medication errors should be reported to Pfizer Safety within 24 hours on a CT SAE Report Form **only when associated with an SAE.**

8.4. Treatment of Overdose

For this study, any dose of PF-06651600 greater than 800 mg within a 24-hour time period will be considered an overdose.

There is no specific antidote or specific treatment for an overdose.

In the event of an overdose, the investigator should:

- 1. Contact the Medical Monitor within 24 hours.
- 2. Closely monitor the participant for any AE/SAE and laboratory abnormalities for at least 5 half-lives or 28 calendar days after the overdose of PF-06651600 (whichever is longer).

- 3. Obtain a plasma sample for PK analysis within 4 days from the date of the last dose of study intervention if requested by the Medical Monitor (determined on a case-by-case basis).
- 4. Document the quantity of the excess dose as well as the duration of the overdose in the CRF.
- 5. Overdose is reportable to Safety only when associated with a SAE.

Decisions regarding dose interruptions or modifications will be made by the investigator in consultation with the Medical Monitor based on the clinical evaluation of the participant.

8.5. Pharmacokinetics

During all study periods, blood samples (\sim 2 mL) to provide plasma for PK analysis will be collected into appropriately labeled tubes containing dipotassium ethylenediaminetetraacetic acid (K₂EDTA) anticoagulant at times specified in the Schedule of Activities section of the protocol.

Blood will be collected at the time points identified in the Schedule of Activities section of the protocol. All efforts will be made to obtain the pharmacokinetic samples at the exact nominal time relative to dosing. For each blood sample collection, the allowable windows are as follows for time post dose: $0.5 \text{ hr} (\pm 10 \text{ min})$, $1 \text{ hr} (\pm 15 \text{ min})$ and $3 \text{ hr} (\pm 30 \text{ min})$. The date and exact time of the sample collection is to be noted on the source document and data collection tool (eg, CRF), as well as the date and time of the previous dose. Samples obtained outside the windows specified in the Schedule of Activities will be considered a protocol deviation.

- The plasma will be stored in appropriately labeled screw-capped polypropylene tubes at approximately -20°C or colder within 1 hour of collection.
- Further details regarding the collection, processing, storage and shipping of the blood samples will be provided in the lab manual.
- Samples will be analyzed using a validated analytical method in compliance with Pfizer standard operating procedures.
- The PK samples must be processed and shipped as indicated to maintain sample integrity. Any deviations from the PK processing steps, including any actions taken, must be documented and reported to the sponsor. On a case-by-case basis, the sponsor may make a determination as to whether sample integrity has been compromised. Any sample deemed outside of established stability, or of questionable integrity, will be considered a protocol deviation.
- As part of understanding the pharmacokinetics of the study intervention, samples may be used for metabolite identification and/or evaluation of the bioanalytical method. These data will be used for internal exploratory purposes and will not be included in the clinical report. These additional exploratory analyses will not be performed on samples collected from participants at sites in China; refer to Section 10.7.2.

8.5.1. Shipment of Pharmacokinetic Samples

The shipment address and assay lab contact information will be provided to the Investigator site prior to initiation of the study. The central laboratory will provide collection materials and directions for packaging and shipment of samples and will forward samples to the contract analytical laboratory.

8.6. Pharmacodynamics

Blood samples (~2.5 mL) will be collected for measurements of immunoglobulin (Ig) (IgA, IgG, IgM) at the time points listed in the Schedule of Activities.

Blood samples (~5.0 mL) will be collected by fluorescence activated cell sorting (FACS) analysis to identify T cell, B cell, and natural killer (NK) cell (FACS-TBNK) subsets at the time points listed in the Schedule of Activities.

As part of understanding the PD of the study intervention, samples may be used for evaluation of the bioanalytical method, as well as for other internal exploratory purposes. These additional exploratory analyses will not be performed on samples collected from participants at sites in China; refer to Section 10.7.2.

Samples will be analyzed using fit for purpose or validated analytical methods in compliance with applicable Pfizer standard operating procedures. The pharmacodynamic (PD) samples must be processed and shipped as indicated in the instructions provided to the investigator site to maintain sample integrity. Any deviations from the PD sample handling procedure (eg, sample collection and processing steps, interim storage or shipping conditions), including any actions taken, must be documented and reported to the sponsor. On a case-by-case basis, the sponsor may make a determination as to whether sample integrity has been compromised.

8.7. Genetics

8.7.1. Specified Genetics

Genetics (specified analyses) are not evaluated in this study.

8.7.2. Banked Biospecimens for Genetics.

Banked biospecimens for genetics are not included in this study.

8.8. Biomarkers

Biomarkers are not evaluated in this study.

8.8.1. Specified Gene Expression (RNA) Research Specified gene expression (RNA) research is not included in this study.

8.8.2. Specified Protein Research

Specified protein research is not included in this study.

8.8.3. Specified Metabolomic Research

Specified metabolomic research is not included in this study.

8.8.4. Banked Biospecimens for Biomarkers

Banked biospecimens for biomarkers are not included in this study.

8.9. Medical Resource Utilization and Health Economics

Medical resource utilization and health economics data, associated with medical encounters, will be collected in the CRF by the investigator and study-site personnel for all participants throughout the study. Protocol-mandated procedures, tests, and encounters are excluded.

The data collected may be used to conduct exploratory economic analyses and will include:

- Data collected in the Alopecia Areata Resource Utilization (AARU)
- Number and duration of medical care encounters, including surgeries, and other selected procedures (inpatient and outpatient)
- Duration of hospitalization (total days or length of stay, including duration by wards [eg, intensive care unit])
- Number and type of diagnostic and therapeutic tests and procedures

9. STATISTICAL CONSIDERATIONS

See Appendix 10 for vaccine sub-study statistical considerations.

9.1. Estimands and Statistical Hypotheses

There is no formal statistical hypothesis testing for this study.

9.1.1. Estimands

Not applicable to this study.

9.2. Sample Size Determination

Sample size is not based on any formal hypothesis testing but instead driven by the regulatory requirement for the safety database. Sample size is determined by the number of participants who enroll from the Phase 2a Study (B7931005) and participants who enroll from the Phase 2b/3 Study (B7981015), as well as the number of de novo participants enrolled. It is estimated that a total of approximately 960 participants will be enrolled in Study B7981032, including approximately 450 de novo participants. The number of de novo participants enrolled may be modified based on the actual number of participants who continue from Study B7931005 and Study B7981015 into Study B7981032.

9.3. Populations for Analyses

For purposes of analysis, the following populations are defined:

Population	Description
Enrolled	All participants who sign the ICF.
Safety	The Safety Analysis Set (SAS) is defined as all participants who received at least 1 dose of study intervention.
Efficacy	The Full Analysis Set (FAS) is defined as all participants, regardless of whether they received study intervention.
PK	The PK concentration population is defined as all enrolled participants who received at least 1 dose of PF-06651600 and in whom at least 1 concentration value is reported.

9.4. Statistical Analyses

The statistical analysis plan will be developed and finalized before database lock and will describe the participant populations to be included in the analyses, and procedures for accounting for missing, unused, and spurious data. Data analysis for participants who permanently discontinued treatment but remained in the study (Section 7.1.1) will be described in the statistical analysis plan. This section is a summary of the planned statistical analyses of the primary and secondary endpoints.

9.4.1. Timing of the Analyses

The PCD clinical study report (CSR) will include analyses of the following:

- All safety data collected through the PCD (Section 4.4).
- Efficacy data collected for the time points as specified in the applicable SoAs through the Month 36 visit for each participant.

The supplemental CSR will include analyses of the following:

- All safety data collected in the entire study.
- Efficacy data collected for the time points post Month 36 visit, as specified in the applicable SoA of TP2.

9.4.2. Efficacy Analyses

For the purpose of analysis of efficacy measures for the participants originating from the index studies, the baseline values are defined as the Day 1 values from Study B7981015 or B7931005. For assessments which were not collected in the respective index study, the baseline value is defined as the value collected on Day 1 of Study B7981032. For the de novo participants, the baseline values are defined as the values collected on Day 1 of Study B7981032.

PCD CSR			
Endpoint	Statistical Analysis Methods		
Primary	There are no primary efficacy endpoints.		
Secondary	Efficacy analyses are descriptive in nature (such as number and percent, mean, standard deviation) at each visit where measured; there will be no formal hypothesis testing, though 95% two-sided confidence intervals will be reported. Displays by de-novo participants (ie, those who did not receive study intervention in either Study B7931005 or B7981015) and participants originating from Study B7931005 or B7981015 (ie, those who received study intervention in either Study B7931005 or B7981015) will also be included.		
	For participants who permanently discontinue from study intervention but remain in the study, efficacy data collected during the observation period (see Section 7.1.1.1) will be included in efficacy listings, but not in the efficacy summaries.		
	Further details will be specified in the statistical analysis plan.		
Exploratory	Will be described in the statistical analysis plan.		
Supplemental	CSR		
Endpoint	Statistical Analysis Methods		
Primary	There are no primary efficacy endpoints.		
Secondary	There are no secondary efficacy endpoints.		
Exploratory	Efficacy analyses are descriptive in nature There will be no formal hypothesis testing.		
	For participants who permanently discontinue from study intervention but remain in the study, efficacy data collected during the observation period (see Section 7.1.1.1) will be included in efficacy listings, but not in the efficacy summaries.		
	Further details will be specified in the statistical analysis plan.		

For both the PCD CSR and the supplemental CSR the endpoints for SALT include both the SALT overall and SALT AA scores.

The SALT overall score includes any hair loss regardless of etiology (eg, including scalp hair loss due to both androgenetic alopecia and AA). The SALT AGA score only takes into account scalp hair loss due to androgenetic alopecia. The SALT AA score at each visit will be calculated as follows using the applicable SALT AGA score collected at the last visit of the treatment period (as defined in Section 8.1.2.1.1):

SALT AA Score = SALT overall score – SALT AGA score

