1.3. Schedule of Activities (SoA)

De novo participants are defined as those who did not previously receive study intervention in Study B7931005 or B7981015; this includes, but is not limited to, those consented and screened for Study B7931005 or B7981015 but who did not receive study intervention in one of these studies.

Participants originating from Study B7931005 or B7981015 are defined as those who received study intervention in one of these studies.

A = De novo participants;

B = Participants originating from Study B7931005 or B7981015 with >30 days between the first visit of Study B7981032 and the last dose in Study B7931005 or B7981015;

C = Participants originating from Study B7981015 with >14 days to ≤ 30 days between the first visit of Study B7981032 and the last dose in Study B7981015;

D = Participants originating from Study B7981015 with \leq 14 days between the first visit of Study B7981032 and the last dose in Study B7981015;

E = All participants originating from Study B7931005;

X = All participants

See Appendix 10 for vaccine sub-study schedule of activities.

If participant visits or procedures are affected by a public emergency, including the coronavirus disease 2019 (COVID-19) pandemic, please refer to Appendix 13.

1.3.1. Screening and Day 1

Screening is only applicable for de novo participants (Group A) and participants originating from Study B7931005 or B7981015 with >30 days between the first visit of Study B7981032 and the dose in Study B7931005 or B7981015 (Group B). The screening visit date is defined as the date that informed consent/assent is obtained for Study B7981032.

Procedures conducted as part of the participant's routine clinical management (eg, chest x-ray or other appropriate diagnostic imaging such as computed tomography or magnetic resonance imaging [MRI]) and obtained before signing of the ICF may be utilized for screening or baseline purposes provided the procedures met the protocol-specified criteria and were performed within the time frame defined in the SoA. This includes procedure(s) which were completed for participants consented and screened for study B7981015 but who did not receive study intervention in study B7981015. Separate informed consent/assent for Study B7981032 must be obtained prior to use of data in Study B7981032 per Section 10.1.3.

Procedure	Screening	Day 1	Notes
Visit Window (±Days)	None	None	
Visit Identifier	1	2	
Day	-35 to -1	1	
Enrollment procedures			

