HBVDNA (applicable countries)	A, B		For de novo participants and participants originating from Study B7931005 or B7981015 with >30 days between the first visit of Study B7981032 and the last dose in the index study, testing will be dependent on the screening results from Study B7981032. See Appendix 7 for Japan specific requirements. Section 8.2.8.5, Appendix 6
Varicella Zoster Virus immunoglobulin G antibody (VZV IgG Ab) (adolescents only, if applicable)	A, B		VZV IgG Ab is only required in adolescent participants 12 to <18 years of age without documented evidence of having received varicella vaccination (2 doses). Serological testing must be performed for VZV IgG Ab only in the absence of documented evidence of having received varicella vaccination (2 doses) per Exclusion #16. Section 8.2.8.3, Appendix 2

Procedure	Screening	Day 1	Notes
Collection of sample for potential viral screen		A, E	For participants from Study B7981015 a sample will be collected for Study B7981032 if it was tested in Study B7981015. Section 8.2.8.4, Appendix 2
Screening tuberculosis test	A, B		Exclusion Criterion 19 in Section 5.2.2, Section 8.2.8.1, Section 8.2.8.1.2, Appendix 2
Day 1 tuberculosis testing/chest radiograph		C, D	Section 8.2.8.1, Section 8.2.8.1.2, Appendix 2
Pharmacodynamics marke	ers		
FACS-TBNK		A, B	Section 8.6
Immunoglobulins (IgA, IgG, IgM)		A, B	Section 8.6
Trial treatment			
IRT registration	A, B	C, D	
IRT study intervention assignment		X	
Study intervention dispensing		X	Section 6.2
Study intervention administration		X	Section 6.1
Clinical assessments			
SALT	A, B	A, B	Section 8.1.2.1.

Procedure	Screening	Day 1	Notes
AA eligibility assessment	A, B	A, B	Scalp hair loss due to AA to be assessed to verify eligibility for de novo participants and participants originating from Study B7931005 or B7981015 with >30 days between the first visit of Study B7981032 and the last dose of study intervention in Study B7931005 or B7981015. Section 8.1.2.1.2.
EBA and ELA	A, B	A, B	Section 8.1.2.2, Section 8.1.2.3
Photography	A, B	A, B	Section 8.1.4
Assessment of Fingernails Affected by AA		A, B, E	Collected at Day 1 in all de novo participants, all participants originating from B7931005, and participants originating from Study B7981015 with >30 days between the first visit of B7981032 and the last dose in Study B7981015. Section 8.1.2.4
CGI-AA	A, B	A, B	Section 8.1.2.5

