2.2.3.1. Phase 2a Study in Alopecia Areata

Study B7931005 was a Phase 2a, double-blind, placebo-controlled, multicenter study to evaluate the efficacy and safety profile of PF-06651600 and PF-06700841 (a TYK2/JAK1 inhibitor) compared with placebo in adult (18-75 years old) participants with AA with scalp hair loss of ≥50% at baseline. The study consisted of an initial 24-week double-blind treatment period, an up to 12-month extension period, and a 6-month cross-over open label extension period. A total of 142 participants were randomized to study treatment: 47 participants received placebo, 48 participants received PF-06651600, and 47 participants received PF-06700841.

During the initial 24-week treatment period, participants randomized to PF-06651600 were treated with 200 mg QD during a 4-week induction phase followed by dosing with 50 mg QD in a maintenance phase. The primary efficacy endpoint in the study was change from baseline in Severity of Alopecia Tool (SALT) score at Week 24. Analysis of the initial 24-week treatment period provided data on both efficacy and safety, and indicated clinical improvement with PF-06651600. PF-06651600 met the primary endpoint of change from baseline (CFB) in SALT score. The Mixed Model for Repeated Measures (MMRM) estimates for PF-06651600 compared to placebo at Week 24 for SALT mean CFB (95% CI) were 33.6 [95% CI= (21.4, 45.7); Hochberg p (1-sided) <0.0001]. PF-06651600 differentiated from placebo (statistically significant), as early as Week 6. The placebo response was almost negligible. PF-06651600 also differentiated from placebo on the proportion of responders in absolute SALT score ≤10, eyelash assessment (ELA) and eyebrow assessment (EBA).

During the initial 24-week treatment period of Study B7931005, there were no deaths and no participant in the PF-06651600 treatment group experienced a serious adverse event (SAE). The proportion of participants who experienced treatment-emergent adverse events (TEAEs) in the placebo treatment group (74.5%) was comparable with the PF-06651600 treatment group (62.5%). The TEAEs reported in more than 5% of participants with AA receiving PF-06651600 were headache, infections of upper respiratory tract, acne, diarrhea, nausea, and skin infections. The majority of events were mild. No serious infections, malignancies, cases of herpes zoster, or cases of herpes simplex were reported in the PF-06651600 group.

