5.1.2. Inclusion Criteria for All Participants Originating from B7931005 or B7981015

The following inclusion criteria must be met for all participants originating from B7931005 and B7981015.

Prior B7931005 or B7981015 Clinical Study Experience

- 2. Participants enrolling from Study B7931005 must have:
 - Taken the last dose of PF-06700841 (a TYK2/JAK1 inhibitor) in Study B7931005 >12 weeks prior to the Study B7981032 Day 1 visit.
- 3. Participants enrolling from Study B7981015 must have:
 - Completed ≥34 weeks of study intervention.

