9.4.3. Safety Analyses

All safety analyses will be performed on the Safety Population. For the purpose of analysis of safety measures for the participants with ≤30 days between the first visit of Study B7981032 and the last dose of study intervention in the index studies, the baseline values are defined as the Day 1 values from Study B7981015 or B7931005. For the de novo

participants and participants with >30 days between the first visit of Study B7981032 and the last dose of study intervention in the index study, the baseline values are defined as the values collected on Day 1 of Study B7981032.

PCD CSR	
Endpoint	Statistical Analysis Methods
Primary	The primary endpoints of incidence of TEAEs, SAEs, and AEs leading to discontinuation, clinically significant abnormalities in vital signs, and clinically significant abnormalities in laboratory values will be summarized using descriptive measures such as numbers and percentages. The safety summaries will be reported for all participants, as well as by de-novo participants (ie, those who did not receive study intervention in either Study B7931005 or B7981015) and participants originating from Study B7931005 or B7981015 (ie, those who received study intervention in either Study B7931005 or B7981015).
	No formal statistical hypotheses will be tested.
	Further details will be specified in the Statistical Analysis Plan.
Secondary	There are no secondary safety endpoints.
Exploratory	There are no exploratory safety endpoints.
Supplemental	CSR
Endpoint	Statistical Analysis Methods
Primary	There are no primary safety endpoints.
Secondary	The secondary endpoints of incidence of TEAEs, SAEs, and AEs leading to discontinuation, clinically significant abnormalities in vital signs, and clinically significant abnormalities in laboratory values will be summarized using descriptive measures. The safety summaries will be reported for all participants, as well as by de novo participants and participants originating from Study B7931005 or B7981015.
	No formal statistical hypotheses will be tested.
	Further details will be specified in the statistical analysis plan.
Exploratory	There are no exploratory safety endpoints.

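### For rollovers who took PF-06700841, or never took PF-06651600, in B7931005, the index-study Day 1 baseline counts change on another drug or off treatment as PF-06651600 efficacy

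*Protocol*

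**What the plan says.** Protocol Section 9.4.2 sets one efficacy baseline rule for everyone who comes from an index study: "the baseline values are defined as the Day 1 values from Study B7981015 or B7931005". The only exception concerns missing instruments, where the B7981032 value is used: "For assessments which were not collected in the respective index study, the baseline value is defined as the value collected on Day 1". Displays are split into de novo and originating participants, with no split by prior compound or by gap.

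Section 5.1.2 shows that some of these people took a different JAK inhibitor. Its condition for entry from B7931005 is: "Taken the last dose of PF-06700841 (a TYK2/JAK1 inhibitor) in Study B7931005 >12 weeks prior to the Study B7981032 Day 1 visit". Section 2.2.3.1 gives the initial allocation there: "47 participants received placebo, 48 participants received PF-06651600, and 47 participants received PF-06700841". It also describes an extension of up to 12 months and a 6-month cross-over open-label extension, without saying who took which drug in them.

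Section 1.3 defines the group with a longer gap, counted from the final index-study dose: "B = Participants originating from Study B7931005 or B7981015 with >30 days between the first visit of Study B7981032 and the last dose". The two groups with gaps of 30 days or less contain B7981015 participants only, so the Schedule of Activities leaves B7931005 rollovers in Group B. Group B has SALT, EBA and ELA at screening and on Day 1, and the note on eligibility, which for rollovers is limited to gaps over 30 days, reads: "Scalp hair loss due to AA to be assessed to verify eligibility for de novo participants and participants originating from Study B7931005 or B7981015".

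For the same long-gap participants, Section 9.4.3 takes the other choice for safety: "the baseline values are defined as the values collected on Day 1 of Study B7981032". Appendix 11 does likewise for its rule on worsening SALT in the VHP countries.

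**The concern.** A baseline for PF-06651600 efficacy should precede PF-06651600 and little else. For someone treated with PF-06700841 in B7931005, index Day 1 precedes a course of another active drug and a washout of more than 12 weeks. For someone who received only placebo there, it precedes a period with no PF-06651600 at all. Whatever happened to the hair in that time becomes part of the reported change from baseline.

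The endpoints exposed are those that compare with baseline: change in SALT, SALT75, SALT50, and the 2-grade route to EBA or ELA response. The affected participants are pooled with all other originating participants, so a reader of the report could not see or remove their contribution.

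**Working it through.** The plan gives no sample size, power or precision figure that depends on the efficacy baseline, so there is nothing to reproduce. The check bounds what can be carried in from before the first B7981032 dose.

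**Inputs**
- Index SALT, b: 50 to 100, since B7931005 required "scalp hair loss of ≥50% at baseline" (Section 2.2.3.1).
- Re-entry SALT, r: at least 25, from the 25% rule at screening and Day 1 for a gap over 30 days (Section 5.1.1). SALT AGA is taken as 0 (assumption).
- Rollovers: about 960 − 450 = 510 (Section 9.2).
- Randomised to PF-06700841 in B7931005: 47.

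**Step 1. Improvement already present at B7981032 Day 1 = b − r, largest at r = 25**

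| Index SALT | Largest carried-in improvement | As % of index |
|---|---|---|
| 50 | 50 − 25 = 25 | 50.0% |
| 75 | 75 − 25 = 50 | 66.7% |
| 90 | 90 − 25 = 65 | 72.2% |
| 100 | 100 − 25 = 75 | 75.0% |

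SALT50 can be met on arrival from any index score of 50 or more. SALT75 can be met on arrival only at one point, index 100 with re-entry exactly 25. With B7981032 Day 1 as baseline, the carried-in change is 0 by construction.

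**Step 2. Effect on later response.** Take index 100 and re-entry 30.
- SALT75 needs a score of 0.25 × 100 = 25 from the index baseline, an on-study gain of 30 − 25 = 5 points.
- From B7981032 Day 1 it needs 0.25 × 30 = 7.5, a gain of 30 − 7.5 = 22.5 points.
- If the participant reaches 20, change is 20 − 100 = −80 from index and 20 − 30 = −10 from Day 1.

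**Step 3. The opposite direction.** Take index 60, re-entry 90, later 60. Change is 60 − 60 = 0 from index and 60 − 90 = −30 from Day 1. Here the index baseline hides a 30-point gain.

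**Step 4. Scale in the originating display (illustration only).** Suppose all 47 participants randomised to PF-06700841 enrolled and each carried in 25 to 75 points of improvement. They would be 47/510 = 9.2% of rollovers, and mean SALT change would move by 47/510 × 25 = 2.3 to 47/510 × 75 = 6.9 points. Neither assumption can be checked, and carried-in worsening would move the mean the other way.

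**The case against.** The index baseline has a sound rationale for most originating participants. For anyone who took PF-06651600 in the index study, index Day 1 is the true pre-treatment value, and change from it is a fair measure of cumulative long-term benefit. It also matches PGI-C and P-Sat, which ask originating participants to look back to the start of the index study (Sections 8.1.3.2 and 8.1.3.3). Moving everyone with a gap over 30 days to B7981032 Day 1 would discard real drug effect, or count hair regained after an off-drug relapse as new improvement. This part of the objection stands and confines the point to people without that rationale.

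Several stronger readings are tempting and are not supported:
- **That efficacy is biased upward.** The documents do not say whether SALT at re-entry is above or below index values. The 25% rule also keeps out anyone with less hair loss than that, including the best earlier responders.
- **That participants arrive as SALT75 responders.** That needs the single limiting case in the table.
- **That 47 + 47 = 94 people are affected.** That counts initial assignment to placebo or PF-06700841. Enrolment and extension-period drugs are not given.
- **That inclusion criterion 2 shows PF-06700841 was the last drug taken.** It is a washout rule only.
- **That placebo starters in B7981015 are affected too.** They moved to active drug after Week 24, and rollovers need at least 34 weeks of study intervention.
- **That the safety rule proves the efficacy rule wrong.** The two serve different purposes. It shows only that a Day 1 baseline is workable for this group.

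Two limits also stand. The study tests no hypothesis, has no primary efficacy endpoint and shows de novo participants separately. And the only SAP supplied covers the vaccine sub-study, so a main-study SAP could contain a sensitivity baseline. Section 9.4.2 nevertheless states the baseline outright and does not leave it to the SAP.

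**Conclusion.** The point holds for originating participants whose B7931005 drug was PF-06700841, or who never received PF-06651600 there. Applied as written, Section 9.4.2 attributes to PF-06651600 any change on the other drug and during the washout.

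Per person, carried-in improvement is bounded by 25 to 75 points depending on index SALT, assuming no androgenetic component. Carried-in worsening is equally possible. The effect on the originating-group summary cannot be determined from the documents; the 2.3 to 6.9 points above illustrates scale and is not an estimate. De novo results do not change, and absolute SALT ≤10 and ≤20 use no baseline. This is a modest flaw in descriptive secondary and exploratory results, worth correcting because the needed values are already collected.

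**What to change.** In Section 9.4.2, and in the main-study SAP:

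1. For originating participants whose index-study drug was PF-06700841, or who never received PF-06651600 in the index study, define the B7981032 Day 1 value as baseline for all baseline-dependent efficacy endpoints. Show index-baseline results as supportive.
2. State how a participant who took both compounds across the B7931005 periods is classified.
3. For other participants with a gap over 30 days, keep the index baseline and add a supplementary summary from B7981032 Day 1.
4. Report how many participants fall under each rule.

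The cost is a change of wording in the protocol and SAP and one extra derivation, with no new data collection. The downside is a second baseline to explain for a small subgroup, in whom SALT change would run from a different date than PGI-C and P-Sat. A footnote on those tables would deal with that.
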